## 7.0 STUDY AGENT ADMINISTRATION OR INTERVENTION AND TOXICITY MANAGEMENT PLAN

- 7.1 At each appointment where dental treatment is indicated with concurrent use of the virtual reality system, the virtual reality goggle set will be tested prior to the appointment by a resident or staff member to ensure it is working properly. A brief conversation will be had between the provider, parent, and patient regarding what dental treatment will be rendered that day, and an overview of how the virtual reality system works. The parent and child will be informed that they can choose to stop use of the virtual reality system at any point during the procedure if they wish to withdraw from the study for any reason. Once all questions have

been answered, the virtual reality set will be placed on the patient's face prior to beginning any treatment. The virtual reality goggle system will remain in place until the end of sealant placement for half the mouth, or until treatment is aborted due to poor cooperation, or any other relevant concerns. All indicated dental treatment will be completed to the standard of care, and the child will be asked at the completion of treatment if any adverse effects from the virtual reality were experienced.

7.2 Criteria for removal from the virtual reality distraction are outlined below.

7.21 If the virtual reality system fails due any technological error with the equipment itself during the dental appointment.

7.22 The patient becomes uncooperative, and dental treatment cannot be rendered safely.

7.23 The patient experiences any sign of physical discomfort related to the virtual reality system such as headache, dizziness, claustrophobia, or any other symptoms.

7.24 A patient may always be removed from treatment whenever he/she wishes.

7.3

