## 6.0 STRATIFICATION/DESCRIPTIVE FACTORS/RANDOMIZATION SCHEME

- 6.1 The participants in the study will serve as their own control using a split mouth cross-over randomized control clinical trial design and will be randomly assigned to receive virtual reality or traditional behavior guidance techniques during dental sealant placement. Patients will serve as their own control. Stratification between sites will not be done.
- 6.2 Patient characteristics that will be considered include demographic data such as age, gender, previous dental experience, and number of hours per week the child spends having “screen time”. Additionally, complexity/difficulty of treatment being rendered will be recorded (how many sealants were placed). The dental resident will determine the child’s behavior using the Frankl behavior rating scale at the initial exam, and each subsequent appointment while the child is enrolled in the study.

- 6.3 Randomization will be achieved using an envelope system. Envelopes will be labeled 1 through 52 on the exterior and will serve as the patient's coded study ID. Each envelope will be filled with a single paper slip indicating Group 1, Group 2, Group 3, Group 4. The groups are listed below which takes into account randomization of VR, basic behavioral guidance techniques (BBG), site of mouth. Equal amount of each groups will be represented in the total stack of envelopes. The order of envelopes within the stack will be random. When a child and their parent agree to enroll in the study, an envelope will be drawn from the randomized stack, and the category inside will be assigned to that patient.

	First half of appointment	Second half of appointment
Group 1	VR with right side sealants	BBG with left side sealants
Group 2	VR with left side sealants	BBG with right side sealants
Group 3	BBG with right side sealants	VR with left side sealants
Group 4	BBG with left side sealants	VR with right side sealants

- 6.4 Carryover effect will be reduced by allowing a short rest time between starting the second half of the sealants. For instance, if VR is used first, after finishing sealants on one side of the mouth with VR, the headset will be removed. The patient will then be given 3-5 minutes break before starting the sealants on the second half of the mouth. Carryover effect will also be reduced by randomizing if patients will receive VR for the first half of sealants placed or for the later half.

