## 8.0 ASSESSMENT OF EFFICACY AND SAFETY

8.1 Side effects to be monitored:

8.11 Possible symptoms to be monitored during use of the virtual reality device include dizziness, altered, blurred or double vision, eye or muscle twitches, disorientation, anxiety attack, excessive sweating, nausea, lightheadedness, motion sickness, convulsion. If patient reports any of the following symptoms, use will be discontinued immediately.

8.12 Long term monitoring will not be required, as there are no lasting effects of short-term use of the virtual reality device.

8.2 Adverse Event Reporting:

8.21 Any adverse events will be addressed immediately, recorded, and reported where appropriate within 24 hours.

8.22 Parents, if not present in the operatory during the procedure, will be informed immediately of any adverse events.

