#### 12.0 DATA COLLECTION AND MONITORING

Each patient will be given a study ID number (the number labeled on the exterior of the random envelope they are assigned) and the physical master list of all participants will be kept in a separate location from the data (in a binder located at Children's Dental Health Clinic at Long Beach Memorial Resident Room or USC pediatric graduate clinic). See Appendix A.

A Frankl score will also be assigned to each patient by the providing dentist at the end of each appointment and recorded in the Dentrix software where patient electronic health records are kept at the Children's Dental Health Clinic at Long Beach Memorial or Axium software at USC's pediatric graduate clinic.

After consenting to participation in the research, the patient and parent will be asked the patient's average weekly "screen time" which will be recorded in the Dentrix/Axium treatment note for their initial exam appointment.

Each patient will wear a pulse-oximeter during dental treatment appointments. The heart will be reported verbally at outlined steps during the procedure and analyzed at a later date. The person viewing the video will record the verbally reported heart rate and at each step into the data collection sheet (see Appendix B).

The providing dentist will ask the patient at the end of the treatment, for research purposes, if any adverse side effects were experienced during VR use and include it in the Dentrix/Axium treatment note for that appointment.

The data from the parent satisfaction survey and healthcare provider questionnaire will be obtained electronically through Qualtrics and the data will be transferred to an excel sheet stored in USC OneDrive. There will be no paper versions of the data collected. The excel sheet will be kept and secured until the end of the study, at which point it will be deleted. See Appendix B.

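### The only solicited side-effect question comes once, at the end of the visit, and covers VR only, so late-disclosed symptoms are collected after a sequence-dependent delay and have no control-half comparator

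*Protocol*

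**What the plan says.** Three places in the protocol describe one solicited question about side effects.

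- Section 7.1: "the child will be asked at the completion of treatment if any adverse effects from the virtual reality were experienced".
- Section 12.0: the dentist "will ask the patient at the end of the treatment, for research purposes, if any adverse side effects were experienced during VR use", and the answer goes into the treatment note.
- Section 9 calendar: the row for VR side effects runs into its neighbour in the text at hand. The only mark shown is under End of Treatment, with none under the VR or basic behavior guidance columns. Section 9 places End of Treatment 5 minutes after the last sealant.

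Other provisions also bear on safety capture.

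- Section 8.11 opens with "Possible symptoms to be monitored during use of the virtual reality device include dizziness" and continues with a list of further symptoms. It adds: "If patient reports any of the following symptoms, use will be discontinued immediately".
- Section 7.23 makes physical discomfort related to the headset a reason for removal from VR.
- Section 8.21: "Any adverse events will be addressed immediately, recorded, and reported where appropriate within 24 hours". This is not limited to VR or to one half of the visit.

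On sequence, Section 6.3 gives VR first in Groups 1 and 2 and second in Groups 3 and 4, and states: "Equal amount of each groups will be represented in the total stack of envelopes". On the gap between halves, Section 6.4 states: "The patient will then be given 3-5 minutes break".

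**The concern.** Each child goes through both conditions in one visit, and the order is randomized. Most outcomes are collected in pairs: the calendar marks heart rate, FPS-R, FLACC and Frankl under both conditions, and Appendix A has separate parent surveys for VR and standard care. Solicited side effects are the exception. They are asked about once, about VR only, at a moment whose distance from VR depends on the sequence.

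Two things follow for symptoms first mentioned at that question. A VR-first child has had a break and a complete control procedure since the headset came off, so a symptom that began in the control half can be put down to VR. And because no matching question covers the control half, there is no background rate to read the VR count against. Several listed symptoms, such as nausea, sweating and lightheadedness, could plausibly also arise during dental treatment, and the child, who may be as young as 6, is left to judge the cause.

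What is at stake is how far the pilot can describe the tolerability of the headset. A later analysis plan cannot recover answers to questions that were not asked.

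**Working it through.** The protocol gives no figure for the timing of this question, so there is none to reproduce. The check is arithmetic on its stated durations.

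**Inputs**

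| Input | Value | Source |
|---|---|---|
| Break between halves | 3-5 min | Section 6.4 |
| VR half | about 5-10 min | Section 3.0 |
| Control half | 5-10 min | Assumption: same as the VR half; not stated |
| Last sealant to End of Treatment | 5 min | Section 9 |
| Sample size | 40 | Sections 3.0 and 13.1 |
| Envelopes | 52, in four equal groups | Section 6.3 |

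**Delay from the end of VR to the question**

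- VR second: delay = wait after the last sealant = 5 min (0 min if the question is put as soon as the last sealant is placed).
- VR first: delay = break + control half + wait.
  - Shortest: 3 + 5 + 5 = 13 min. Longest: 5 + 10 + 5 = 20 min.
  - Without the final wait: 3 + 5 = 8 min to 5 + 10 = 15 min.

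**Difference between sequences**

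- With the wait: 13 - 5 = 8 min to 20 - 5 = 15 min.
- Without it: 8 - 0 = 8 min to 15 - 0 = 15 min.

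The gap is about 8-15 minutes on either reading of when the question is asked.

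**How many children have the longer delay**

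The stack holds 52 / 4 = 13 envelopes per group, so 2 x 13 = 26 of 52 are VR-first. With 40 children the expected number is 40 x 26/52 = 20, or half.

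**What is captured, by period**

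| Period | Solicited symptom question | Other capture |
|---|---|---|
| While VR is worn | None at the time | Monitoring (8.11), removal for discomfort (7.23), any adverse event (8.21) |
| Break after VR, VR-first children | None | Any adverse event, unprompted (8.21) |
| Control half | None | Any adverse event, unprompted (8.21); video |
| End of Treatment | One, about VR only | Any adverse event, unprompted (8.21) |

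The parent surveys and provider questionnaire in Appendix A ask about pain and about distress or anxiety. They do not ask about the physical symptoms in 7.23 and 8.11. The gap is therefore confined to symptoms not noticed or volunteered at the time and first disclosed at the closing question.

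**The case against.** A reader might infer that VR symptoms cannot be told apart from symptoms of dental treatment at all. The documents do not support that. Section 8.11 requires monitoring during VR and acts on a report at once, and Section 7.23 acts on discomfort related to the headset, so such events are tied to the VR half when they happen. Section 8.21 records any adverse event in either half. Video covers both halves, so visible events can be placed. Anxiety, one of the overlapping symptoms, is assessed under both conditions.

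A reader might also infer that the side-effect count is materially biased by recall. That is not shown either. The gap is 8-15 minutes within one visit and rests partly on an assumed control-half duration. The question itself is worded to limit the answer to VR. Any count of falsely attributed symptoms would need a background rate and an attribution rate, and the protocol gives neither.

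It can fairly be added that comparative tolerability is not an objective: Section 2.0 covers behavior, pain and anxiety, and the pilot is descriptive. The Appendix B data sheets are not in the text at hand, so the recording detail cannot be fully judged.

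These arguments narrow the point but do not remove it. Monitoring under 8.11 is tied to use of the device, and 8.21 sets no question. Relying on 8.21 for the control half would set prompted VR reports against unprompted control reports. A VR-first child who feels unwell in the break is not asked before the control half begins.

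**Conclusion.** The point holds in a limited form. Sections 7.1 and 12.0 and the calendar consistently fix one solicited question, at the end and about VR only. For symptoms first disclosed there, about half the children answer some 8-15 minutes later after VR than the other half, with a control procedure in between, and no background rate exists from the control half. The size of the gap rests on the assumption that the control half lasts 5-10 minutes.

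The consequence is a less interpretable description of tolerability. It does not bear on the Frankl or heart-rate comparison, and it does not mean that symptoms arising during VR go unrecorded. It is a modest, inexpensive improvement to data collection, and it has to be made before enrolment to be of use.

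**What to change.** In Sections 7.1, 9 and 12.0:

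1. Ask one brief, neutrally worded symptom question, with no mention of VR, immediately after the VR half and again immediately after the control half. Use the same words both times.
2. Record the answer by half, and mark it in the calendar under both the VR and basic behavior guidance columns.
3. Tabulate reports by condition and by sequence.
4. Keep the closing question about VR as an extra.

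This removes the sequence-dependent delay and supplies the control-half comparator. The monitoring and discontinuation provisions in 7.2 and 8.1 are untouched. A symptom checklist before treatment is not recommended: it could prime anxiety, which the trial measures.

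The cost is about a minute per half and an entry for each half on the data sheet. Systematic asking will probably raise the number of mild symptoms reported. There is a small chance that asking between halves affects the second half; this applies equally in both sequences.

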## 8.0 ASSESSMENT OF EFFICACY AND SAFETY

8.1 Side effects to be monitored:

8.11 Possible symptoms to be monitored during use of the virtual reality device include dizziness, altered, blurred or double vision, eye or muscle twitches, disorientation, anxiety attack, excessive sweating, nausea, lightheadedness, motion sickness, convulsion. If patient reports any of the following symptoms, use will be discontinued immediately.

8.12 Long term monitoring will not be required, as there are no lasting effects of short-term use of the virtual reality device.

8.2 Adverse Event Reporting:

8.21 Any adverse events will be addressed immediately, recorded, and reported where appropriate within 24 hours.

8.22 Parents, if not present in the operatory during the procedure, will be informed immediately of any adverse events.

8.23 Places for submitting reports: IRB, Co-Investigators

## 9.0 CLINICAL AND LABORATORY EVALUATIONS AND STUDY CALENDAR

The Pre-treatment appointment will be the comprehensive or periodic exam where the patient is identified as a good candidate for participation in the study, and agrees to enroll.

End of Treatment will be all dental sealants are placed and 5 minutes has elapsed since the end of sealant placement.

Post- treatment is any date after the treatment has been completed when the parameters can be analyzed, and any remaining treatment and/ or follow-up appointments can be completed.

SC= Standard of Care

RP= Research purposes

Parameter	Pre-Treatment	VR Distraction	Basic Behavior Guidance	End of Treatment/Study Participation	Post-Treatment
Comprehensive Medical History	X (SC)	X (SC)	X (SC)		
Report of Average Weekly Screen Time	X (RP)				
Virtual Reality Distraction		X (RP)	X (RP)		
Heart Rate measured by Pulse-Oximeter		X (RP)	X (RP)		
Video Recording of Dental Appointment		X (RP)	X (RP)		
Self- Reported Scores (FPS-R)		X (RP)	X (RP)		
FLACCS		X (RP)	X (RP)		

Frankl Score completed by provider	X (SC)	X (SC)	X (SC)		
Health Care Provider Questionnaire					
Satisfaction Survey completed by parents/guardianHealth Care Provider Questionnaire				X (RP)	
Report of experienced VR side effectsSatisfaction Survey completed by parents/guardian				X (RP)	
Scoring of behaviors displayed on video				X (RP)	

#### 10.0 CRITERIA FOR EVALUATION AND ENDPOINT DEFINITIONS

The outcome status (behavior) of all eligible patients will be reported.

Frankl Score: Patient's behavior as rated by the dental provider within one of the following categories: 1= definitely negative, 2= negative, 3= positive, 4= definitely positive. This scale is routinely used by dentists and documented in the patient chart.

Behavior, and anxiety will be scored at the following time points:

- Baseline (patient sitting in the chair prior to treatment)
- During sealant placement with virtual reality distraction
- During sealant placement with basic behavior guidance
- Post Operative (patient sitting upright in chair, 5 minutes post completion of dental sealant placement)

Anxiety: Measured by change in heart rate at outlined points (above) during restorative procedure.

Completion of Dental Treatment: Was the treatment able to be completed, or was the appointment aborted due to patient cooperation, complication with virtual reality system, or any other reason.

Parent Satisfaction Survey: Will be evaluated post treatment for the Virtual Reality and standard of care. Satisfaction questions will be asked on a scale on a scale of 1 to 10. (Appendix A. Figure 3.1 and 3.2)

Healthcare Provider Questionnaire: Will be obtained after each session, completed by the provider performing treatment. (Appendix A. Figure 4)

#### 11.0 SPECIAL INSTRUCTIONS:

Not applicable

#### 12.0 DATA COLLECTION AND MONITORING

Each patient will be given a study ID number (the number labeled on the exterior of the random envelope they are assigned) and the physical master list of all participants will be kept in a separate location from the data (in a binder located at Children's Dental Health Clinic at Long Beach Memorial Resident Room or USC pediatric graduate clinic). See Appendix A.

A Frankl score will also be assigned to each patient by the providing dentist at the end of each appointment and recorded in the Dentrix software where patient electronic health records are kept at the Children's Dental Health Clinic at Long Beach Memorial or Axium software at USC's pediatric graduate clinic.

After consenting to participation in the research, the patient and parent will be asked the patient's average weekly "screen time" which will be recorded in the Dentrix/Axium treatment note for their initial exam appointment.

Each patient will wear a pulse-oximeter during dental treatment appointments. The heart will be reported verbally at outlined steps during the procedure and analyzed at a later date. The person viewing the video will record the verbally reported heart rate and at each step into the data collection sheet (see Appendix B).

The providing dentist will ask the patient at the end of the treatment, for research purposes, if any adverse side effects were experienced during VR use and include it in the Dentrix/Axium treatment note for that appointment.

The data from the parent satisfaction survey and healthcare provider questionnaire will be obtained electronically through Qualtrics and the data will be transferred to an excel sheet stored in USC OneDrive. There will be no paper versions of the data collected. The excel sheet will be kept and secured until the end of the study, at which point it will be deleted. See Appendix B.

## 13.0 STATISTICAL CONSIDERATIONS

13.1 The objectives of this study are to explore the associations between the use of virtual reality distraction during dental sealant placement with Frankl score, and anxiety based on change in heart rate via video recording, when compared to the control group.

The study design is a randomized controlled trial with a crossover split-mouth design where each patient will serve as both the experimental group and the control.

This is a pilot study. Data analyzed will be changed in heart rate between baseline and sealant placement using virtual reality or behavior guidance technique.. No statistical analysis will be conducted except mean and range.

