This is a pilot study. Data analyzed will be changed in heart rate between baseline and sealant placement using virtual reality or behavior guidance technique.. No statistical analysis will be conducted except mean and range. Other factors will also be analyzed including timing of virtual reality intervention (1st vs. 2nd half of the appointment), age, gender, previous dental experience, and average amount of "screen time" a child is allowed per week.

The demographic factors will be collected from the patient's medical chart. Ethnicity will not be collected.

The parent will be asked “how many hours of “screen time” (TV, computer, video games, tablet use), would you say that your child is allowed per week?” and this will be recorded with their coded Study ID number during the recruitment phase. See Coded ID and data sheet in section 13.2. Parents will also be asked to complete a satisfaction survey after the Virtual Reality appointment and the Standard of Care appointment. (Appendix A. Figure 3.1 and 3.2)

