### 1. VR and Frankl Score

Null Hypothesis: There is no difference in Frankl Score between a visit where virtual reality is used and a visit where basic behavior guidance is used during dental sealant placement.

Alternative Hypothesis: Frankl score will improve when virtual reality distraction is used during dental sealant placement.

Sample Size: N=40

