### 2. VR and Anxiety based on Heart Rate

Null Hypothesis: There is no difference in heart rate at each step of a dental restorative procedure when virtual reality is being used during dental sealant placement. .

Alternative Hypothesis: The heart rate is lower at each listed step of the dental procedure when virtual reality is used as a behavior management technique during dental sealant placement.

13.2 Female and male participants as well as patients of all racial/ethnic backgrounds will be recruited equally. The USC graduate pediatric dental clinic accepts patients ages 0-15 of all backgrounds, and each child that fits the inclusion criteria for the study will be offered to enroll. The Children's Dental Health Clinic at Long Beach Memorial. accepts patients is an all inclusive dental home to children

and young adults from birth through age 21, and each child that fits the inclusion criteria for the study will be offered to enroll.

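### The mean-and-range rule conflicts with the protocol's own hypotheses and leaves the within-child VR effect with no measure of uncertainty

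*Protocol*

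**What the plan says.** - **The rule.** Section 13.1 states "No statistical analysis will be conducted except mean and range". Section 3.0 repeats it, and both places call the study a pilot.
- **The data covered.** The sentence just before the rule reads "Data analyzed will be changed in heart rate between baseline and sealant placement using virtual reality or behavior guidance technique". Frankl score is not named there.
- **The hypotheses.** Section 13 then gives a null and an alternative for each of two outcomes. For behavior the alternative is that "Frankl score will improve when virtual reality distraction is used during dental sealant placement". For heart rate it is that "The heart rate is lower at each listed step of the dental procedure when virtual reality is used". Section 1.2 hypothesises that VR does better than BBG on pain and anxiety, and the primary objective in Section 2.1 compares behavior under the two.
- **The factors.** Directly after the rule, Section 3.0 says "Other factors will also be analyzed including timing of virtual reality intervention", followed by age, gender, previous dental experience and screen time.
- **The design.** Each child receives both conditions in one appointment. Section 6.3 randomises four groups that cross order (VR first or second) with mouth side. The planned size is 40, with no derivation given.

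**The concern.** A null and a directional alternative call for some statement of how sure one can be about a difference. A mean and a range for each condition do not supply it. The rule is a positive exclusion that appears twice, so a later analysis plan that added an interval or a test would contradict the protocol.

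Three conflicts follow:

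1. The hypotheses ask for a verdict that the permitted output cannot give.
2. The primary objective is behavior, and the first hypothesis concerns Frankl score, but the sentence naming the data analysed covers heart rate only.
3. Relating outcome to age or weekly screen time needs more than a mean and range, unless children are cut into subgroups.

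At stake is whether a randomised trial in 40 children can say anything about its own questions, and whether it passes on the one quantity that a later crossover trial most needs, the SD of the within-child differences.

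**Working it through.** **1. The plan's own figure.** N = 40 cannot be reproduced, because the protocol gives no alpha, power, effect size, SD or within-child correlation. This is not evidence that 40 is wrong.

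**2. What means by condition keep.** Let V and B be a child's heart rate under VR and BBG, and let b be that child's single pre-treatment baseline. The difference in change is (V − b) − (B − b) = V − B, so the baseline cancels. With all 40 children complete, mean(V) − mean(B) = mean(V − B). The paired point estimate is therefore retained.

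**3. What they lose.** The variance of V − B depends on how the values pair within children, and condition means and ranges do not show this. A constructed example with n = 40 has mean change 10 bpm under BBG (range −22.6 to 35.4) and 6 bpm under VR (range −12.0 to 22.4). The same values were paired in two ways:

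| Pairing | Mean difference | SD of differences | 95% CI | p |
|---|---|---|---|---|
| Ordered | −4.0 | 3.9 | −5.2 to −2.8 | <0.001 |
| Shuffled | −4.0 | 14.1 | −8.5 to 0.5 | 0.08 |

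The output that the protocol allows by condition is identical in both rows, although one is a clear effect and the other is inconclusive.

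**4. Precision if the paired difference were reported.** The half-width is t(0.975, 39) × SD_diff / √40 = 2.023 / 6.325 × SD_diff = 0.32 × SD_diff. After adjusting for order and side (37 df) the multiplier is still 0.32. To express this in bpm, take SD_diff = SD × √(2(1 − ρ)), where SD (per condition) and ρ (between conditions) are assumptions:

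| Assumed SD (bpm) | ρ = 0 | ρ = 0.5 | ρ = 0.7 | ρ = 0.9 |
|---|---|---|---|---|
| 8 | 3.6 | 2.6 | 2.0 | 1.1 |
| 12 | 5.4 | 3.8 | 3.0 | 1.7 |
| 16 | 7.2 | 5.1 | 4.0 | 2.3 |

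**5. Order and side.** The stack holds 52 envelopes, 13 per group, so 26 put VR first. If 40 are used at random, an exact 20/20 split on order has probability 0.257. A split no worse than 23/17 has probability 0.257 + 2 × (0.210 + 0.113 + 0.039) = 0.981. With an assumed 5 bpm drift between halves, a 23/17 split moves the raw VR contrast by 5 × (23 − 17)/40 = 0.75 bpm. Even with perfect balance, an unmodelled drift of that size raises an assumed SD_diff of 9.3 to √(9.3² + 5²) = 10.6. The effect is mainly a loss of precision, with a small bias possible.

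**The case against.** The strongest reply is that this is a declared pilot meant to explore associations, and descriptive reporting is acceptable in a pilot. That stands. The defect is the mismatch with formal hypotheses, and recasting those as descriptive aims would remove that contradiction. It would not supply the paired SD.

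A reader might infer more than the documents support:

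- **That randomised order is thrown away.** Section 3.0 lists VR timing for analysis, under the same limit. Only side is in no analysis statement.
- **That the pairing is thrown away.** Change from the child's own baseline is a within-child quantity, and step 2 shows that the paired point estimate survives with complete data. Nothing forbids giving the mean and range of each child's difference. Since the expected range of 40 normal values is about 4.3 SD, that would yield a rough paired SD. But the protocol does not say it will summarise differences, and a range rests on two children.
- **That VR cannot be separated from half or side.** Equal numbers of the four groups in the stack balance both approximately, and means by group are allowed.
- **That ignoring the pairing has a fixed price, such as 44%.** With an assumed SD of 12 and ρ = 0.7 on raw heart rate, the half-widths are 2.97 paired and 1.991 × 12 × √(2/40) = 5.34 unpaired, a 44% reduction. If ρ = 0.7 also holds with baseline, the planned change score has SD 9.3 and the unpaired figure is 1.991 × 9.3 × √(2/40) = 4.1, a reduction of about 28%. The plan computes neither interval.

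A mixed model for every numeric score, or a covariate for number of sealants, would be a preference and not a correction.

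**Conclusion.** The point holds in this form: the mean-and-range rule, stated twice and tied to heart-rate change alone, contradicts the Frankl and heart-rate hypotheses, the comparative behavior objective and the planned factor analyses. Followed as written, the trial yields a VR-minus-BBG point estimate with no uncertainty attached, so its hypotheses can be neither supported nor rejected.

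This conclusion rests on the text and needs no assumed number. Its size can be given without assumptions only as ±0.32 SD_diff at n = 40. The bpm figures depend on an SD and a correlation that the protocol does not give. The statement that the paired point estimate is kept assumes complete data. If treatment is aborted in one half, which Section 10.0 provides for recording, the two condition means come from different sets of children and the identity fails.

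The documents do not support the stronger conclusions that the design is wasted, that VR is confounded with order or side, or that 40 is the wrong number.

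**What to change.** Replace the sentence in both Section 3.0 and Section 13.1:

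1. **Heart rate.** Report the within-child VR-minus-BBG difference in change, with its SD and a 95% CI, accounting for randomised order and side. A regression of the 40 differences on order and on the side treated under VR is enough. The four groups cross these two factors, so both terms can be estimated.
2. **Frankl score.** Add it to the named data. Report how many children scored better, the same or worse under VR, with an exact interval. Expect many ties, because enrolment requires F3 or F4, and report their number.
3. **Other factors.** Say that timing, age, gender, previous dental experience and screen time will be described, and how.
4. **Status.** Label all of these as pilot estimates. If no formal test is intended, reword the hypotheses in Section 13 as exploratory aims.

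The data are already to be collected under the protocol. The cost is protocol wording and a few hours of analysis.
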